## 8 IMMUNOGENICITY ANALYSIS

### 8.1 Populations Analyzed

The number and percentage of participants in each analysis population (randomized, exposed, safety, mITT, IEP) are summarized by treatment group for all participants. Reasons for exclusion from analysis populations are summarized by treatment group for all randomized participants and listed by participant.

### 8.2 Demographics and Baseline Characteristics

#### 8.2.1 Demographics

Demographic and baseline characteristics including age, age stratum, sex, race, ethnicity, baseline height, weight and body mass index, and baseline anti-CHIKV SNA serostatus (positive or negative) are tabulated by treatment group for the randomized, safety, mITT, and IEP populations for both age groups pooled and by age strata. Participant site assignment is evident from the unique participant identifier.

#### 8.2.2 Baseline Disease Characteristics

This study enrolls healthy US adolescent and adult participants  $\geq 65$  years of age, so no baseline disease characteristics are collected.

### **8.2.3 Medical History**

Medical history is coded to the MedDRA dictionary SOC and PT (see Section 5.8). A summary table and a listing of medical history are supplied by treatment group for the randomized population.

### **8.2.4 Prior and Concomitant Medications and Vaccines**

Prior medications are defined as those taken within 30 days prior to the screening visit (90 days for blood products) through the start of IP administration on Day 1 (baseline). Concomitant medications are defined as those taken after start of IP administration on Day 1 (baseline) through the end of study. See definitions in Section 6.3. Partial dates are imputed according to Section 6.5.2.

Prior and concomitant medications and vaccines are coded to the WHO Drug Global Dictionary ATC classification and preferred drug name (see Section 5.8). All prior and concomitant medications and vaccines are tabulated together by ATC classification, preferred drug name, and treatment group for the safety population; a second similar table contains only concomitant vaccines. A participant data listing of all prior and concomitant medications is generated.

## **8.3 Treatment Compliance**

As the IP administration is a single 0.8 mL intramuscular injection performed by site personnel, measurements of treatment compliance are not applicable. A vaccine administration summary is provided and details listed.

## **8.4 Immunogenicity Analysis**

Summary statistics for immunogenicity results by scheduled visit for each treatment group are provided for the IEP and mITT populations, unless otherwise specified. Anti-CHIKV SNA seroresponse rates and GMTs are tabulated by visit for each treatment group. Geometric mean fold increase as well as number and percentage of participants meeting anti-CHIKV SNA titers of  $\geq 15$  and 4-fold rise from baseline are also displayed by post-vaccination scheduled visit for each treatment group. Reverse cumulative distribution plots of anti-CHIKV SNA titer versus percentage of participants in each treatment group are generated by scheduled visit for the IEP. Anti-CHIKV SNA GMT are also plotted over time for each treatment group for the IEP.

The primary analysis of all immunogenicity endpoints utilizes the IEP across both age groups combined. As specified for individual endpoints below, primary and secondary immunogenicity analyses of anti-CHIKV SNA seroresponse rates and GMTs are repeated using the mITT population as a measure of robustness of results. All immunogenicity analyses are repeated in the separate age strata for the IEP, and primary and secondary immunogenicity analyses of anti-CHIKV SNA seroresponse rates and GMTs are repeated in the separate age strata for the mITT population as well. No multiplicity adjustment is made for the analysis of the mITT population or of the separate age strata as the primary population is the combined age groups in the IEP.

In addition, the primary immunogenicity endpoints using the IEP across both age groups combined are repeated by sex, by race group (white and non-white), and by ethnicity group (Hispanic or Latino and Not Hispanic or Latino). If the baseline (Day 1) seropositive rate is  $\geq 10\%$ , then subgroup analyses will be performed by baseline serostatus (positive or negative) for coprimary immunogenicity endpoints as well as key secondary seroresponse rate endpoints.

Finally, two types of sensitivity analysis for the coprimary endpoints (difference in anti-CHIKV SNA seroresponse rate between PXVX0317 and placebo at Day 22 and GMTs at Day 22) are performed as described in Section 6.5.3. These endpoints are recalculated using the conservative imputation methods for missing immunogenicity outcome data at Day 22 (i.e., nonresponder analysis and LOCF analysis) and reported for the mITT population to assess the robustness of primary endpoint results to informative missingness.

#### **8.4.1 Coprimary Immunogenicity Endpoints**

##### **8.4.1.1 Day 22 Treatment Group Estimates and Difference in Anti-CHIKV SNA Seroresponse Rates**

The superiority of PXVX0317 vaccine immunogenicity over that of placebo is illustrated at Day 22 by estimating the treatment-specific seroresponse rates and by calculating the difference in seroresponse rates between the two treatment groups (the percentage of participants with an anti-CHIKV SNA titer [REDACTED]; PXVX0317 minus placebo) and associated 95% CI. See Section 6.1 for statistical details.

This endpoint is summarized for both age strata pooled and for individual age strata in the IEP, as well as by sex, by race group (white and non-white), and by ethnicity group (Hispanic or Latino and Not Hispanic or Latino) for both age strata pooled in the IEP. The analysis, both for the pooled age strata and for individual age strata but not for subgroups, is repeated using the mITT population as a measure of robustness of results. Additionally, sensitivity analyses of this endpoint are performed using the mITT population as described in Section 6.5.3.

A forest plot is generated to represent seroresponse rate differences between treatment groups at Day 22 for the IEP, both for pooled age strata and for individual age strata.

##### **8.4.1.2 Day 22 Anti-CHIKV SNA GMT by Treatment Group**

Day 22 anti-CHIKV SNA GMTs and associated 95% CIs are compared between PXVX0317 and placebo treatment groups to demonstrate superiority of PXVX0317 vaccine. See Section 6.1 for statistical details.

This endpoint is summarized for both age strata pooled and for individual age strata in the IEP, as well as by sex and by race group (white and non-white) and ethnicity group (Hispanic or Latino and Not Hispanic or Latino) for both age strata pooled in the IEP. The analysis, both for the age strata pooled and for individual age strata but not for subgroups, is repeated using the mITT population as a measure of robustness of results. Additionally, sensitivity analyses of this endpoint are performed using the mITT population as described in Section 6.5.3.

A graph of anti-CHIKV SNA GMTs by visit is presented for the IEP population. As well, a reverse cumulative distribution plot of titers by visit is displayed for the IEP population.

#### **8.4.2 Secondary Immunogenicity Endpoints**

##### **8.4.2.1 Key Secondary Immunogenicity Endpoints: Treatment Group Estimates and Difference in Anti-CHIKV SNA Seroresponse Rates at Day 15 and Day 183, in that order**

The key secondary endpoint of treatment specific anti-CHIKV SNA seroresponse rates and treatment group difference in seroresponse rates (PXVX0317 minus placebo) and associated 95% CI based on antibody titers measured at Day 15 and Day 183 will be analyzed as described above for Day 22. For each time point, the null hypothesis of no difference between seroresponse rate percentages in the PXVX0317 vs. placebo group is tested using a chi-square test with alpha=0.05.

This endpoint is summarized for both age strata pooled and for individual age strata using the IEP. The analyses are repeated using the mITT population as a measure of robustness of results. Additionally, sensitivity analyses of these endpoints are performed using the mITT population as described in Section [6.5.3](#).

##### **8.4.2.2 Anti-CHIKV SNA GMT at Day 15 and Day 183 by Treatment Group**

The secondary endpoint of anti-CHIKV SNA GMT and associated 95% CIs for PXVX0317 and placebo based on antibody titers measured at Day 15 and Day 183 is analyzed as described above for Day 22.

This endpoint is summarized for both age strata pooled and for individual age strata using the IEP. The analyses are repeated using the mITT population as a measure of robustness of results.

##### **8.4.2.3 GMFI in Anti-CHIKV SNA Titer from Day 1 to Days 15, 22 and 183 by Treatment Group**

Geometric mean fold increase over Day 1 (baseline) titer is analyzed as described for GMTs for each post-vaccination time point (Days 15, 22 and 183) by treatment group. See Section [6.1](#) for statistical details and definition of anti-CHIKV SNA assay in Section [6.3](#) for handling of anti-CHIKV SNA titer values below LLOQ.

This endpoint is summarized for both age strata pooled and for individual age strata using the IEP population. Geometric mean fold increase is plotted by visit for the IEP, and a reverse cumulative distribution of fold-rise from baseline by visit is also presented for the IEP.

##### **8.4.2.4 Participants with Anti-CHIKV SNA Titer $\geq 15$ and 4-fold Rise over Baseline at Days 15, 22 and 183 by Treatment Group**

Number and percentage of participants with an anti-CHIKV SNA titer  $\geq 15$  and 4-fold rise over Day 1 (baseline) at Days 15, 22 and 183 are analyzed by treatment group as described for Day 22 seroresponse. See Section [6.1](#) for statistical details.

This endpoint is summarized for both age strata pooled and for individual age strata using the IEP.

#### **8.4.3 Exploratory Immunogenicity Endpoint**

##### **8.4.3.1 Geometric Mean Titers for Neutralizing Antibodies against Various CHIKV Genotypes at Day 22**

For a subset of participants in the PXVX0317 group (CHIKV genotype subset, see Section 5.3), baseline (Day 1) and Day 22 samples are tested for neutralizing antibodies against various CHIKV genotypes. GMTs and associated two-sided 95% CIs are reported for this participant subset, along with fold change relative to the LR2006 OPY-1 strain. This analysis may be performed as a Clinical Study Report Addendum.

### **8.5 Pharmacokinetic and Pharmacodynamic Analysis**

Not applicable.

## **9 SAFETY ANALYSIS**

All safety data are presented in the form of tabulations and participant listings, based on the safety population.

### **9.1 Extent of Exposure**

The frequencies and percentages of participants receiving IP administration are summarized by treatment group for the randomized population, along with whether or not the dose was administered per protocol (yes/no).

### **9.2 Adverse Events**

The safety of PXVX0317 in healthy adult participants  $\geq 65$  years of age is evaluated using solicited AEs occurring from IP administration on Day 1 through Day 8, unsolicited AEs through Day 29, and AESI and SAEs and MAAEs through Day 183 EOS. AEs are coded to SOC and PT according to the MedDRA dictionary per Section 5.8. They are coded for severity according to Section 5.9 and Appendix II. Only treatment-emergent AEs are summarized (i.e., excluding those after a participant has given informed consent, but before vaccination). See Section 6.3 for definitions.

Solicited AEs, unsolicited AEs, AESI and SAEs and MAAEs are summarized separately by treatment group and maximum severity for the safety population for both age strata combined. Separate participant data listings of solicited and unsolicited AEs sorted by participant identifier and AE start date are generated.

### **9.2.1 Overall Summary of Solicited and Unsolicited Adverse Events**

A high-level summary of solicited and unsolicited AEs combined reviews the frequency counts and percentages of participants by treatment group reporting AEs in each of the following categories:

- Any AE and any AE  $\geq$ Grade 3
- Any solicited AE and any solicited AE  $\geq$ Grade 3
- Any treatment-related solicited AE and any treatment-related solicited AE  $\geq$ Grade 3
- Any unsolicited AE and any unsolicited AE  $\geq$ Grade 3
- Any treatment-related unsolicited AE and any treatment-related unsolicited AE  $\geq$ Grade 3
- Any SAE
- Any treatment-related SAE
- Any AE leading to study discontinuation
- Any fatal AE
- Any AESI (see definition in Section 6.3)
- Any MAAE and any treatment-related MAAE

In addition, summaries of combined solicited and unsolicited AEs by SOC, PT and highest reported severity are provided for the following populations:

- Safety population, both age groups
- Safety population by age strata
- Safety population by sex
- Safety population by race group
- Safety population by ethnicity

### **9.2.2 Solicited Adverse Events from Day 1 until Day 8**

Solicited AEs recorded daily in the e-diary or paper diary until Day 8 include local (i.e., pain, redness, and swelling) and systemic reactions (i.e., fever, chills, fatigue, headache, myalgia, arthralgia, and nausea). In addition, solicited AEs ongoing after seven days post-injection (Day 8) and those that are serious or MAAEs are also recorded as unsolicited AEs. Severity of solicited AEs is assessed by the investigator in the same manner as unsolicited AEs.

Frequencies and percentages of participants experiencing each solicited AE are presented by maximum severity and by treatment group. The following summaries of solicited AEs are produced:

- Solicited AEs by maximum event severity, for each event and for any event
- Solicited AEs of severe (Grade 3) or higher severity, for each event and for any event

- Treatment-related solicited AEs by maximum event severity, for each event and for any event
- Day of first onset of solicited AEs, for each event and any event
- Duration of solicited AEs, for each event and any event
- Solicited AEs by day post-injection for each event and for any event

Occurrence of at least one AE by category (local, systemic) for solicited AEs are also included.

The denominator for solicited AE tables comprises only those participants with at least one diary observation (i.e., any non-missing values but excluding “Not done/unknown”), at least one diary observation for a given symptom, or at least one diary observation for a given day, as applicable. ***Note that an elevated in-clinic temperature assessment as part of 30-min post-vaccination vital signs does not count as a solicited AE, as vital signs data are summarized separately.***

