3.2.9 Assess Solicited Adverse Events

Electronic or paper diaries (memory aids) will be used to collect solicited AEs following vaccination. Participants will record events in their diary daily, for at least seven days after vaccination. Solicited AEs to be assessed in this study are local events of pain, redness, and swelling at the injection site and systemic events of oral temperature $\geq 38.0^{\circ}\text{C}$ ($\geq 100.4^{\circ}\text{F}$), chills, fatigue, headache, myalgia, arthralgia, and nausea.

Participants will be trained to complete a diary (electronic or paper) to observe, measure, and record these solicited AEs daily. A digital thermometer will be provided to the participants to measure their temperature each day. The highest temperature measured each day should be recorded in the participant's diary or memory aid (electronic or paper). To record injection site local reactions, a ruler will be provided to the participant to measure and record the diameter of redness and swelling at the largest point of the reaction each day.

Study staff will review the signs and symptoms recorded in the diary or memory aid (electronic or paper) daily and will follow-up with participants if any data is missing. The investigator will then assess all solicited AEs for severity (Section 8.1.8) and the action taken, and causality (Section 8.1.9). The results of the investigator's assessment will be recorded as a separate source document and will be entered on the solicited AE eCRF.

Symptoms continuing beyond the solicited AE collection period will be collected and recorded on the AE eCRF.

Details on safety definition, evaluation, reporting periods and documentation are outlined in Section 8.

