3.2.10 Assess Unsolicited Adverse Events

Unsolicited AEs (AEs not listed in the diary or memory aid [electronic or paper]) will be collected from Day 1 through 28 days post vaccination.

Details on safety definition, evaluation, reporting periods and documentation are outlined in Section 8.

3.2.11 Assess Serious Adverse Events, Medically Attended Adverse Events, and Adverse Events of Special Interest

Serious Adverse Events, AESI, and MAAE will be collected for all participants from Day 1 through Day 183 End of Study Visit.

Details on safety definition, evaluation, reporting periods, and documentation are outlined in Section 8.

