9.6.4.1 Adverse Events

Adverse events will be coded to the MedDRA dictionary SOC and PT. They will be graded for severity according to Section 8.1.8. Only treatment-emergent AEs will be collected (ie, those after the start of IP administration). Adverse events will be reported using both age strata pooled, but selected AE analyses will be repeated for the separate age strata. All AE tabulations and participant listings will be based on the safety population.

Solicited AEs, unsolicited AEs, MAAEs, AESI, and SAEs will be summarized separately by treatment group and SOC, PT, and maximum severity for the safety population for both age strata combined. Only participants with at least one solicited AE observation (ie, any nonmissing values but excluding “not done/unknown”) will be summarized. Solicited AEs continuing beyond seven days after IP administration will be combined with the unsolicited AEs; a combined summary table of solicited and unsolicited AEs by treatment group and SOC, PT, and maximum severity will also be provided for the safety population for both age strata pooled.

Additional AE displays will include the following:

- Solicited AEs \geq Grade 3
- Treatment-related (“possibly”, “probably” or “definitely”) solicited AEs
- Solicited AEs: day of first onset, duration, day postinjection, and occurrence of at least one solicited AE by category (local, systemic)
- Unsolicited AEs \geq Grade 3
- Treatment-related (“possibly”, “probably” or “definitely”) unsolicited AEs

- Medically attended AEs
- Treatment-related MAAEs
- AEs leading to study discontinuation
- Fatal AEs, if any
- Treatment-related (“possibly”, “probably” or “definitely”) SAEs

Separate participant data listings of solicited and unsolicited AEs sorted by participant identifier and AE start date will be generated. Diary compliance will not be summarized.

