## 6.3 Derived Variables

This section provides definitions of the derived variables. In some cases, the definitions are provided in the relevant sections as noted.

**AE, causing study discontinuation**, is defined as a Yes response to the corresponding question on the AE eCRF.

**AE, medically attended (MAAE)**, is defined as a Yes response to the corresponding question on the AE eCRF.

**AE, related**, is defined as one that is “probably” or “possibly” related to IP per investigator assessment on the eCRF. If the relationship is missing for one or more occurrences of an AE for a given participant, the closest relationship of the remaining occurrences of the AE for that participant is used; if the relationship is missing for the only occurrence of an AE for a given participant, then that event is assumed to be related in order to be conservative.

**AE, resulting in death**, is defined as a Yes response to the corresponding question on the AE eCRF and/or a fatal outcome.

**AE, serious**, is defined per the derived eCRF field for AE seriousness, based on the individual criteria that make an AE qualify as serious (results in death, is life-threatening, requires inpatient hospitalization or prolongation of existing hospitalization, results in persistent or significant disability/incapacity, or is a congenital anomaly or birth defect, or any event that may require medical or surgical intervention to prevent one of these outcomes).

**AESI** is defined in this study as new onset or worsening arthralgia that is medically attended, as noted by an AE having a Yes response to the corresponding AESI question on the AE eCRF.

**AE, severity**, is graded Grade 1 (mild) to Grade 4 (potentially life-threatening) as described in Section 5.9. If the severity is missing for one or more occurrences of an AE for a given participant, the maximum severity of the remaining occurrences of the AE for that participant is used; if the severity is missing for the only occurrence of an AE for a given participant, then that event is assumed to be severe in order to be conservative.

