**AEs, solicited**, are defined as those collected in the electronic e-diary or paper diary. Solicited AEs include local (i.e., pain, redness, and swelling) and systemic reactions (i.e., fever, chills, fatigue, headache, myalgia, arthralgia, and nausea). *Solicited AEs were to be entered on Day 1 through Day 8; solicited AEs starting on Day 9 or later will be excluded from tabulations, with the exceptions of AESI and SAEs (see Section 9.2.2 for solicited events collection details).*

The denominator for solicited AE tables comprises only those participants with at least one diary observation (i.e., any non-missing values but excluding “Not done/unknown”), at least one diary observation for a given symptom, or at least one diary observation for a given day, as applicable. *Note that an elevated in-clinic temperature assessment as part of 30-min post-vaccination vital signs does not count as a solicited AE, as vital signs data are summarized separately.*

**AE, treatment emergent**. AE collection begins at Day 1 (baseline), the day of IP administration. AEs occurring after a participant has given informed consent, but before vaccination, are excluded from summaries. Only treatment-emergent AEs are summarized.

**AEs, unsolicited**, are defined as those AEs not listed in the e-diary or paper diary but collected in the EDC. *Unsolicited AEs were to be collected though Day 29 unless they were SAEs, AESI, or MAAEs; unsolicited AEs starting on Day 30 or later that are not SAEs, AESI, or MAAEs are excluded from tabulations (see Section 9.2.2 for solicited vs. unsolicited events).*

Age at screening visit is automatically calculated by EDC based on date of birth versus date of informed consent. Age at baseline (Day 1) is be summarized in all outputs.

**Age group strata** are defined as ages  $\geq 65$  to  $< 75$  and  $\geq 75$  years as randomized. Note that, if a participant is randomized into a stratum and their age is later corrected such that they

should have been placed into a different age stratum, the participant is analyzed according to the corrected age stratum for immunogenicity analyses.

**Analysis visits** are defined in Section [5.5](#).

**Analysis populations** are defined in Section [5.3](#).

**Baseline** is defined in Section [5.6](#). Change from baseline is defined as (value at post-baseline assessment – value at baseline).

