#### **9.2.3 Unsolicited Adverse Events from Day 1 through Day 29**

All unsolicited AEs occurring during the specified collection period in the study are recorded, regardless of their assessment of relatedness by the investigator. Unsolicited AEs include also those solicited AEs ongoing after seven days post-injection (Day 8), AESI, and SAEs.

All reported unsolicited AEs are summarized by treatment group according to MedDRA SOC, PT and highest reported severity. When an unsolicited AE occurs more than once for a participant, the maximum severity and closest relationship to treatment is counted. The unsolicited AE analysis includes unsolicited AEs judged by the investigator as at least possibly related to IP.

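### SAP 9.2.2, SAP 9.2.3 and the protocol differ on when a solicited reaction also counts as an unsolicited AE, and a medically attended reaction resolved by Day 8 can be missed as an MAAE

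*SAP*

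**What the plan says.** Protocol 3.3.1 lists, among the safety endpoints under its primary endpoints, the incidence of unsolicited AEs through Day 29 and of SAEs, MAAEs and AESI through Day 183.

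On which solicited reactions also count as unsolicited:

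- SAP 9.2.2: "solicited AEs ongoing after seven days post-injection (Day 8) and those that are serious or MAAEs are also recorded as unsolicited AEs".
- SAP 9.2.3: "Unsolicited AEs include also those solicited AEs ongoing after seven days post-injection (Day 8), AESI, and SAEs". MAAEs are not named.
- Protocol 9.6.4.1: "Solicited AEs continuing beyond seven days after IP administration will be combined with the unsolicited AEs". No other class of solicited reaction is named.
- SAP 6.3 gives a general definition, that unsolicited AEs "are defined as those AEs not listed in the e-diary or paper diary but collected in the EDC", and closes the entry with a pointer to SAP 9.2.2. Protocol 3.2.10 gives the same kind of definition without that pointer.

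On where the records come from:

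- SAP 6.3: a medically attended AE "is defined as a Yes response to the corresponding question on the AE eCRF".
- Protocol 3.2.9: the investigator's assessment of diary reactions "will be entered on the solicited AE eCRF". The same section then says: "Symptoms continuing beyond the solicited AE collection period will be collected and recorded on the AE eCRF".
- SAP 6.3, under solicited AEs, leaves out of the tabulations those starting on Day 9 or later, except AESI and SAEs. For unsolicited AEs starting on Day 30 or later, the same section keeps SAEs, AESI and MAAEs.

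**The concern.** Two named safety endpoints depend on rules that do not agree. A programmer working from SAP 9.2.2 and one working from SAP 9.2.3 can put the same event in different tables.

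The MAAE count also depends on a form that the protocol does not clearly tell sites to use for every medically attended diary reaction. Sites work from the protocol. A sentence in the SAP about what is recorded cannot create a record that nobody was told to enter.

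At stake are the reproducibility of the unsolicited AE table and the completeness of the MAAE table, in what Protocol 1.7 describes as the first evaluation of this vaccine in elderly adults. No immunogenicity conclusion is affected.

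**Working it through.** The plan states no incidence for this point, so there is no figure to reproduce. The check sets the rules side by side.

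**Step 1. Is a solicited reaction also unsolicited?**

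| Type of solicited reaction | General definition (Protocol 3.2.10; SAP 6.3 before its pointer) | Protocol 9.6.4.1 | SAP 9.2.2 | SAP 9.2.3 |
|---|---|---|---|---|
| Ongoing after Day 8, not medically attended | no | yes | yes | yes |
| Resolved by Day 8, medically attended, non-serious, not arthralgia | no | no | yes | not named |
| Resolved by Day 8, medically attended arthralgia (AESI) | no | no | yes | yes |
| Resolved by Day 8, serious | no | no | yes | yes |
| Resolved by Day 8, not medically attended, not serious | no | no | no | no |

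The two SAP sections differ in the second row alone. The protocol's analysis section also differs from SAP 9.2.2 in the third and fourth rows.

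**Step 2. Does the event reach the AE eCRF?** Protocol 3.2.9 gives a route for symptoms that continue. Protocol 8.4.2 gives one for SAEs and AESI. Protocol 3.2.11 requires MAAEs to be collected for all participants from Day 1 to Day 183 but names no form. For the second row of the table, no protocol section names the AE eCRF, yet SAP 6.3 reads the MAAE flag from it.

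**Step 3. Do the planned tables recover it?** For AESI, SAP 9.3.3 tabulates solicited and unsolicited events together, and Table 14.3.5.10 is titled accordingly. MAAE Tables 14.3.5.11 and 14.3.5.12 have no such statement or counterpart.

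**Step 4. Late onset.** An event handled as a solicited AE that starts on Day 9 or later and is medically attended, but is neither an AESI nor an SAE, is excluded by SAP 6.3. It falls inside the Day 183 MAAE window. If it also has an unsolicited record, as SAP 9.2.2 intends, that record could be kept. The text does not say which provision governs.

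**Step 5. Size, as an illustration.** From the documents: 200 participants planned per arm (SAP 2.2), and 48.0% with a solicited AE in phase 2 Group 8, 50 recipients of the selected dose (Protocol 1.8.1). That study enrolled adults aged 18 to <46 (Protocol 1.4.3). The shares below are assumptions and appear nowhere in the documents.

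- Reactors in the vaccine arm: 200 × 0.48 = 96.
- Medically attended and resolved by Day 8, assumed share 0.5% to 5% of reactors: 96 × 0.005 = 0.48 and 96 × 0.05 = 4.8. That is about 0.5 to 5 participants, or 0.24 to 2.4 percentage points of 200.
- Ongoing after Day 8, assumed share 2% to 20%: 96 × 0.02 = 1.92 and 96 × 0.20 = 19.2. That is about 2 to 19 participants, or 0.96 to 9.6 points. This is an upper limit on the rise in unsolicited incidence, because some of them would have an unsolicited AE anyway.

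**The case against.** The strongest reply is that the SAP has one operative rule. SAP 6.3 points to 9.2.2, SAP 9.2.3 says that unsolicited AEs include certain events without excluding others, and Protocol section 9 calls itself a summary whose details are in the SAP. On this reading 9.2.3 is an incomplete restatement of 9.2.2. This largely disposes of the general definition as a competing rule within the SAP. It does not settle 9.2.3, which gives its own list and leaves out MAAEs.

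On data capture, Protocol 3.2.9 does not forbid entering other reactions on the AE eCRF. Protocol 6.3 and 6.4 list MAAE evaluation beside solicited AE evaluation on Day 1 and Day 15. Protocol 10.3 refers to CRF completion guidelines that are not available here. The title of Table 14.3.5.11 is not restricted to unsolicited events. All of this stands, and it makes the loss of MAAEs a possibility that depends on site practice. It does not supply the missing instruction.

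A missed MAAE would also still appear in the solicited tables by maximum severity. For injection site pain, headache, fatigue and myalgia, an ER visit is Grade 4 in both grading scales, so it would appear in Table 14.3.2.3 as well. What could be lost is its count as an MAAE. Finally, safety endpoints are reported for information only (Protocol 9.4.2, SAP 6.4.2), so no formal test depends on this.

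**Conclusion.** The point holds as an inconsistency that should be reconciled. The class at risk is narrow: non-serious, medically attended solicited reactions other than arthralgia that resolve by Day 8, together with medically attended events handled as solicited that start on Day 9 or later. The first group can be missed as MAAEs if sites follow Protocol 3.2.9 alone. The second can be dropped by the SAP 6.3 exclusion. The size cannot be obtained from the documents and is probably small; the range in the working rests on assumed shares and on a reaction rate from younger adults.

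Three stronger readings are tempting, and the documents do not support them.

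- A reader might infer that unsolicited AE incidence is inflated by reactogenicity. Adding continuing reactions is prespecified in Protocol 9.6.4.1 and in both SAP sections. It raises the count only relative to the general definition, and no arm difference can be derived without an assumed placebo rate.
- A reader might infer that the protocol sends only continuing reactions to the AE eCRF. Protocol 3.2.9 names that route for them and is silent on the rest.
- A reader might infer that the most important vaccine reactions are hidden. SAEs and medically attended arthralgia have their own route to the AE eCRF in Protocol 8.4.2.

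**What to change.** - Align Protocol 3.2.9 and 9.6.4.1 and SAP 6.3 and 9.2.3 with SAP 9.2.2, so that any solicited reaction that is serious, medically attended, an AESI or ongoing after Day 8 is also entered on the AE eCRF.
- Add MAAEs to the exceptions in the SAP 6.3 exclusion of solicited AEs starting on Day 9 or later.
- Count MAAEs from both solicited and unsolicited sources, as Table 14.3.5.10 already does for AESI.
- Keep the prespecified unsolicited tables, and add a row, derived by matching term and date, that shows carried-over solicited reactions separately.

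The cost is wording changes, minor programming and one extra table row. The current SAP describes collection partly in the past tense, so a new eCRF field may come too late; matching term and date avoids one for the extra row. Where a diary reaction was medically attended but has no AE eCRF entry, and the solicited AE eCRF does not hold that information, a site query would be needed to recover it.
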